The proposed study is to compare the pharmacokinetics and pharmacodynamics micro-doses (0.05 and 0.03 mg) of freshly reconstituted Lilly glucagon with Xeris glucagon in healthy volunteers with type 1 diabetes. The hyperinsulinemic-normoglycemic clamp protocol is the standard method to perform pharmacokinetic and pharmacodynamics studies on drugs that effect BG. The doses of glucagon chosen for this study are in the range of doses that are routinely given by the bi-hormonal bionic pancreas. They are expected to result in a modest but easily measureable decrease in the glucose infusion rate (GIR), and will be directly relevant to infusion in the context of a bi-hormonal bionic pancreas. The direct comparison of Lilly glucagon (which has been used in all of the bi-hormonal bionic pancreas studies to date) and Xeris glucagon will provide the

preliminary data required to obtain FDA evaluation of Xeris glucagon in future bionic pancreas studies.

II. Hypothesis and Specific Aims

We hypothesize that Xeris glucagon will be non-inferior to freshly reconstituted Lilly glucagon both in terms of pharmacokinetics (t_{max} , $t_{1/2max}$) and pharmacodynamics (AUC_{GIR}), and in terms of safety. The specific aims of this study are:

Aim 1. To compare the pharmacokinetics and pharmacodynamics of Lilly and Xeris glucagon after low-dose subcutaneous injection using the hyperinsulinemic-normoglycemic clamp technique in volunteers with type 1 diabetes.

Aim 2. To document any adverse events of the Xeris glucagon formulations after subcutaneous injection in volunteers with type 1 diabetes.

III. Subject Selection

III. a. Inclusion Criteria

- Age 21 to 80 years old with type 1 diabetes for at least one year.
- Diabetes managed using an insulin infusion pump using rapid-acting insulin such as insulin aspart (NovoLog), insulin lispro (Humalog), or insulin glulisine (Apidra) for at least one week prior to enrollment.

III. b. Exclusion Criteria

- Unable to provide informed consent.
- Unable to comply with study procedures.
- Current participation in another diabetes-related clinical trial that, in the judgment of the principle investigator, will compromise the results of the clamp study or the safety of the subject.
- Pregnancy (positive urine HCG), breast feeding, plan to become pregnant in the immediate future, or sexually active without use of contraception.
- End stage renal disease on dialysis (hemodialysis or peritoneal dialysis).

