During the hyperinsulinemic-normoglycemic clamp:

- Venous BG measurements
- Timing and size of glucagon doses
- Insulin infusion rate
- Glucose infusion rates
- Plasma insulin levels every 15-30 minutes during the hyperinsulinemic-normoglycemic clamp

- Plasma glucagon levels every 2-15 minutes during the hyperinsulinemic-normoglycemic clamp
- Any adverse events, including nausea, vomiting, pain, and any local reactions to glucagon injection

VI. b. Study Endpoints

Primary endpoint analysis:

- Glucagon t_{\max} for Xeris vs. Lilly (non-inferiority)

Secondary endpoint analyses:

- Area over the curve for glucose infusion rate in the hour following a subcutaneous glucagon dose (AOC_{GIR}) for Xeris vs. Lilly
- Maximal glucose infusion rate (GIR_{\max}) for Xeris vs. Lilly
- Glucagon $t_{\frac{1}{2}\max}$ for Xeris vs. Lilly
- Quantitation of adverse events related to glucagon injection for Xeris vs. Lilly:
 - Injection pain on a 10 cm standard VAS: 0 = no pain, 10 = worst imaginable pain
 - Injection site erythema or other local reaction, maximum diameter within 1 hour of injection
 - Maximal nausea within 1 hour of injection on a 10 cm VAS: no nausea = 0, vomiting = 10

We will calculate means, median, percentages, standard deviations, standard errors, inter-quartile ranges, and 95% confidence intervals in descriptive analyses. We will use paired t-test for comparison of means. We will use multivariate regression models with repeated measurements to compare means and percentages while adjusting for patient demographics characteristics such as age, gender, body mass index, and body surface area.

VI. c. Power Analysis

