Our previous clinical study found a mean $t_{\max} \pm SD$ for Lilly glucagon after subcutaneous injection of 50 mcg of 15.8 ± 3.52 min (Appendix C). A previous pre-clinical PK/PD study in diabetic swine found no significant difference in t_{\max} between Lilly and Xeris glucagon (Appendix B). This study is powered to achieve 90% power to determine non-inferiority of Xeris vs. Lilly glucagon t_{\max} using a one-sided t-test when the margin of equivalence is 2.52 minutes (15% of the t_{\max} for Lilly glucagon in humans) and the true difference between the means of Lilly and Xeris glucagon is assumed to be 0. Therefore, the null hypothesis is that the t_{\max} of Xeris glucagon is not worse than the t_{\max} of Lilly glucagon by more than 2.52 minutes. The assumed standard deviation for each glucagon is 3.52 based on the clinical data. We assume a correlation coefficient between Lilly and Xeris glucagon within the same subject to be 0.7 in this crossover design, resulting in an SD of 2.73 in the difference between the two. The significance level (alpha) of the test is

0.05. The sample size required to achieve the designated power is 12 clamp experiments, each including one injection of Lilly glucagon and one injection of Xeris glucagon.

VII. Risks and Discomforts

There is a potential risk of nausea or vomiting in volunteers due to the administration of exogenous glucagon. The experiments, however, involve small subcutaneous glucagon doses. The recommended dose of glucagon for treatment of severe hypoglycemia in an adult with diabetes is 1000 mcg, given as a single subcutaneous or intramuscular injection. In practice, a smaller dose of 500 mcg is sometimes used initially to reduce the risk of nausea and vomiting. The total dose to be administered in our study is 100 mcg.

There is a potential risk of hypoglycemia, since exogenous insulin will be administered. Given frequent BG monitoring (every two to five minutes), corresponding adjustment of a continuous dextrose infusion, and direct supervision by an NP or MD at all times, the risk of a hypoglycemic episode leading to significant harm to volunteers is expected to be very low. A small meal will be provided to subjects after completion of the study.

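### Section VI.c states the primary null hypothesis backwards: non-inferiority is made the null, against the 90% power in the same paragraph, and no success rule is given

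*Combined protocol and SAP*

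**What the plan says.** The formal statement is in VI.c (Power Analysis): "the null hypothesis is that the t_{\max} of Xeris glucagon is not worse than the t_{\max} of Lilly glucagon by more than 2.52 minutes". The same paragraph gives the purpose of the calculation, "This study is powered to achieve 90% power to determine non-inferiority of Xeris vs. Lilly glucagon", and the method, "using a one-sided t-test when the margin of equivalence is 2.52 minutes". It sets the true difference at 0, the SD of each formulation at 3.52 min, the within-subject correlation at 0.7, the SD of the difference at 2.73 min and alpha at 0.05. It concludes: "The sample size required to achieve the designated power is 12 clamp experiments", each with one injection of each product.

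Two other sections bear on the direction of the test. Section II says: "We hypothesize that Xeris glucagon will be non-inferior to freshly reconstituted Lilly glucagon". Section VI.b lists the primary endpoint as "Glucagon t_{\max} for Xeris vs. Lilly (non-inferiority" and, on method, says only "We will use paired t-test for comparison of means". It gives no sidedness, margin or bound there. The 95% confidence intervals it mentions are for descriptive use and are not tied to the margin.

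**The concern.** Let d be mean t_max for Xeris minus mean t_max for Lilly, with a later peak counted as worse. The plan implies this direction but does not spell it out. The written null is then d ≤ 2.52 min, which is the definition of non-inferiority at that margin. A significance test can only reject its null, so the claim to be demonstrated has to be the alternative.

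Taken literally, a significant result would establish that Xeris is slower by more than the margin, the opposite of the study's aim. A non-significant result would establish nothing. This is the only formal hypothesis in the plan and it belongs to the only powered endpoint. In the text available, no other sentence gives a correct H0/H1 pair or says which result leads to a conclusion of non-inferiority.

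**Working it through.** **Inputs, all from VI.c:** SD per formulation 3.52 min; correlation 0.7; SD of the difference 2.73 min; margin 2.52 min; true difference 0; one-sided alpha 0.05; n = 12.

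**1. SD of the difference.** √(2 × 3.52² × (1 − 0.7)) = 3.52 × √0.6 = 2.727, which agrees with the plan's 2.73.

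**2. Standard error and critical value.** SE = 2.73/√12 = 0.788 min. With 11 degrees of freedom the one-sided 5% critical value is 1.796.

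**3. The plan's N under the conventional null (H0: d ≥ 2.52).** At d = 0 the noncentrality is 2.52/0.788 = 3.20. The noncentral t distribution gives power 0.911 at n = 12, 0.885 at n = 11 and 0.852 at n = 10. Twelve is the smallest n that reaches 90%, so the plan's figure is reproduced.

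**4. The same test under the written null (H0: d ≤ 2.52).** The assumed true difference of 0 lies well inside this null, and the probability of rejecting it is 1.5 × 10⁻⁶. By symmetry, rejection reaches 0.911 only at d = 2 × 2.52 = 5.04 min. The stated power and the stated null cannot describe the same test.

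**5. Cut-offs at the planned SD.** The intended test needs an observed mean difference below 2.52 − 1.796 × 0.788 = 1.10 min. The written null is rejected only above 2.52 + 1.796 × 0.788 = 3.94 min.

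**6. Probabilities by true difference, n = 12:**

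| True d (min) | Intended test concludes non-inferiority | Written null rejected | Written null retained |
|---|---|---|---|
| 0 | 0.911 | 0.0000015 | > 0.999 |
| 2.52 | 0.050 | 0.050 | 0.950 |
| 3.5 | 0.002 | 0.316 | 0.684 |
| 4 | 0.0003 | 0.545 | 0.455 |
| 5.04 | 0.0000015 | 0.911 | 0.089 |

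The last column would be a false-claim rate only if retaining the written null were read as success, which the plan does not say. A simulation of 1,000,000 trials per scenario gave 0.9110 and 0.0497 for the intended test at d = 0 and d = 2.52, and 0.000002 for rejection of the written null at d = 0.

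**7. Level of a confidence-interval rule.** The one-sided 5% test corresponds to the upper limit of a two-sided 90% interval. If the 95% interval mentioned in VI.b were used instead (one-sided 0.025), power at n = 12 would be 0.829 and 90% would need n = 15.

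**8. Margin.** VI.c gives the Lilly mean "after subcutaneous injection of 50 mcg of 15.8 ± 3.52 min (Appendix C"; I.c gives 16.8 min from the same appendix. The margin is defined as 15% of the Lilly mean: 0.15 × 16.8 = 2.52, but 0.15 × 15.8 = 2.37. With 2.37 min, power is 0.879 at n = 12 and 0.904 at n = 13.

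**The case against.** The best reply is that this is a one-word slip. Striking the negative from the sentence puts the null the right way round. The rest of the paragraph gives the aim, the one-sided test, the margin, alpha and N, and these fit only the conventional test. On this view success is already implied: a significant result of that test. Most of the figures for the written null describe a test nobody intended, and the 95% false-claim rate needs a reading that the plan does not state. The 15.8 versus 16.8 min discrepancy is a separate matter.

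Much of this stands. The intent can be recovered, the power calculation used the right null, and N = 12 is sound on its stated inputs. The figures for the written null show that the paragraph contradicts itself; they are not risks the trial will necessarily run. The margin discrepancy does not affect the direction of the null.

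It does not dispose of the point. The rule for the primary claim should be written down, not inferred by setting aside the one sentence that states it. At the planned SD, an observed difference between 1.10 and 3.94 min fails the intended test yet leaves the written null standing, so the rule should be settled before data are seen. The implied rule also leaves the interval level open, and that choice moves power from 0.911 to 0.829.

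**Conclusion.** The concern holds. The null in VI.c is reversed, it contradicts the power statement beside it and the aim in Section II, and no success rule is stated. It must be corrected because it is the decision rule for the primary endpoint. It is an error of specification, not of design: under the conventional null the plan has power 0.911 at n = 12, against 0.0000015 for rejecting the null as written.

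These figures assume normally distributed paired differences, the plan's SD of 2.73 min, a true difference of 0, and alpha of 0.05 one-sided. The last is the reading under which 12 is the smallest n reaching 90%.

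**What to change.** - **VI.c:** replace the sentence on the null with H0: mean t_max(Xeris) − mean t_max(Lilly) ≥ margin, against H1: < margin.
- **VI.b:** state that the primary endpoint is tested by a paired one-sided t-test at alpha 0.05 against that margin. Equivalently, non-inferiority is concluded only if the upper limit of the two-sided 90% confidence interval for the within-subject difference is below the margin. Say that the 95% intervals remain descriptive.
- **Same edit:** reconcile the Lilly mean in VI.c with that in I.c and confirm the margin. If it stays at 2.52 min, nothing else changes. If it becomes 2.37 min, restate power at n = 12 as about 88%; keeping the 90% target would take 13 completed experiments.

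The correction of the null and the success rule costs wording only. N, alpha and data collection are unchanged.

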The study will be conducted by the staff of the MGH Diabetes Research Center (DRC) in cooperation with the staff of the CRC. The PI will conduct meetings with study staff at least twice a month to review study progress, discuss any issues in study conduct, and review procedures. Study staff will be encouraged to raise any concerns they may have or problems they have identified at these meetings. The PI will decide a course of corrective action, and resolution or progress will be assessed no later than the next bimonthly meeting. An audit of procedures, regulatory documentation, and a sample of volunteer files will be performed by a member of the DRC at least biannually. The audit will be conducted by a DRC staff member not directly involved in the conduct of the study. This audit will include a review of regulatory documentation, such as IRB correspondence, and a review of files, including a review of consents, case report forms, and other data from study visits.

A numeric code will be substituted for the volunteers personal identifying information in the study database, which will be password protected. The key linking the medical record number of the volunteer with the numeric code, along with case report forms, and all information that is personally identifiable, will be kept in a locked filing cabinet in an investigator's locked office. All electronic records will be kept in a password protected computer database. All printed computer data will be disposed of confidentially when no longer needed. Only the study staff will have access to the study database. Subjects may not withdraw from the de-identified database, but they may elect to have the key linking their medical record to the de-identified database destroyed.

The study data may be shared with collaborators outside of Partners, but only in a form in which all personally identifiable information has been removed. Shared data will be in the form of a database in which only a number identifies volunteers.

IX. b. Safety Monitoring

A study physician or nurse practitioner will directly supervise each experiment. The PI will be informed of any adverse events immediately and will make any adjustments to the study protocol as needed to maintain subject safety.

The Research Pharmacy will mix the insulin solution. The calculations for the insulin infusion rate and the mixing of the insulin solution will be done in advance and checked by another physician or nurse practitioner.

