This study will be conducted under an Investigational New Drug application sponsored by the PI.

This study is considered moderate risk. The Principal Investigator and co-investigators will evaluate each experiment. Unanticipated problems, including adverse events, will be reported to the Partner's IRB in accordance with the PHRC policy on Unanticipated Problems Involving Risks to Subjects or Others including adverse events. An external Data and Safety Monitoring Board will oversee the conduct of the study and review its results on a regular basis. Additionally, the DSMB will be informed after any experiment that has to be discontinued due to hypoglycemia, hyperglycemia, or any unexpected adverse event. DSMB review will occur before any further experiments are performed. The DSMB will be informed if there are any changes to the study protocol that could significantly impact the safety or scientific validity of the study. A final DSMB meeting will convene after the completion of the study. After the first DSMB meeting, subsequent meetings may be convened via e-mail or conference call. Safety and efficacy data will also be reported to the FDA in compliance with applicable regulations.

IX. c. Adverse Event Reporting Guidelines

The PI will review any adverse events after each experiment. Adverse events will be reported to the Partner's IRB, the DSMB, and to the FDA.

X. Subject Compensation

Financial compensation of \$50 will be provided to all subjects who complete a screening visit. Subjects will be compensated \$250 for participation in the hyperinsulinemic-normoglycemic clamp study visit.

XI. References

[figure not shown]

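### In the visible protocol text, the only DSMB review required before further clamps follows a discontinued clamp; a serious or unexpected reaction in a completed clamp is reported under IX.c, but with no hold and no review deadline

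*Combined protocol and SAP*

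**What the plan says.** The safety provisions are in sections IX.b and IX.c, with related rules in V.d to V.f.

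- **The hold (IX.b).** Beyond regular oversight by an external DSMB, for which no interval is given, "the DSMB will be informed after any experiment that has to be discontinued due to hypoglycemia, hyperglycemia, or any unexpected adverse event". The next sentence reads "DSMB review will occur before any further experiments are performed".
- **Investigator-level safeguards (IX.b).** "The PI will be informed of any adverse events immediately and will make any adjustments to the study protocol as needed to maintain subject safety". Also, "The Principal Investigator and co-investigators will evaluate each experiment".
- **External reporting (IX.b and IX.c).** "Unanticipated problems, including adverse events, will be reported to the Partner's IRB in accordance with the PHRC policy", and "Safety and efficacy data will also be reported to the FDA in compliance with applicable regulations". IX.c adds: "Adverse events will be reported to the Partner's IRB, the DSMB, and to the FDA". The DSMB is also told of protocol changes that could significantly affect safety.
- **Sponsor (IX.b).** "This study will be conducted under an Investigational New Drug application sponsored by the PI".
- **Conduct of the clamp.** A physician or nurse practitioner is on site for the whole clamp (V.f). Injection sites are checked for one hour after each injection and scored on the Draize scale (V.d). If vomiting occurs after both glucagon doses, the clamp may be completed if the subject is willing (V.e).

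**The concern.** The sponsor has already accepted that an unexpected event can justify stopping until the external board has looked at it. As written, that principle applies only if the clamp itself had to be stopped. Whether a clamp is stopped depends on glucose control, venous access, the subject's willingness and whether any dosing remains. None of these measures how serious or how surprising a reaction is. The two can come apart, most easily after the second injection or after the clamp has ended.

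At stake is the order of events: the next subject could receive glucagon before anyone independent of the investigators has considered the reaction. Documenting adverse events of the Xeris formulation is Aim 2 of the study, and IX.b rates the study as moderate risk. No efficacy estimate, error rate or sample size is affected.

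**Working it through.** The plan gives no figure on this point, so the check is mainly a reading of the provisions against possible events.

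**Step 1. What does the hold attach to?** The hold sentence directly follows the discontinuation sentence. Read alone, it could mean review before every experiment, but that would sit badly with a board that reviews results at regular intervals. The natural reading ties it to a discontinued experiment.

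**Step 2. Which events meet the trigger?**

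| Event | IX.b trigger met? | Who is told, on the visible text | Hold before next clamp, on the visible text |
|---|---|---|---|
| Unexpected event that forces the clamp to stop | Yes | PI, DSMB, IRB, FDA | Yes |
| Unexpected local reaction while the clamp runs to completion (no Draize score is linked to stopping) | No | PI at once; DSMB, IRB, FDA under IX.c | None stated |
| Serious event after the clamp has ended, for example once the pump is restarted and dextrose is withdrawn (V.d) | No | As above, if staff learn of it | None stated |
| Vomiting after both doses, clamp completed (V.e) | No | As above | None stated |

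The last row is a known glucagon effect and does not itself call for a hold. It shows only that the plan treats an adverse event and discontinuation as separate things.

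**Step 3. Does another provision supply the hold?** IX.c sends adverse events to the DSMB whether or not the clamp was stopped, but gives no timeline, seriousness tier or pause. The immediate decision rests with the PI, who also sponsors the IND and so is not independent. The IRB policy and FDA regulations are cited but not reproduced.

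**Step 4. Pace of dosing.** Inputs are 12 completed clamps, about 15 performed, over 4-6 months (IV.a). A month is taken as 30.44 days.

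- Fastest: 4 × 30.44 = 121.8 days; 121.8 / 15 = 8.1 days per clamp.
- Slowest: 6 × 30.44 = 182.6 days; 182.6 / 12 = 15.2 days per clamp.

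These are averages. No minimum interval between clamps is written, so the next one could come sooner.

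**Step 5. Dose context.** The Xeris dose here is 50 mcg. The other study described in I.d gave 0.5 and 1.0 mg: 500 / 50 = 10 and 1000 / 50 = 20, so 10 to 20 times as much.

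**The case against.** The strongest reply is that the study is already well guarded and that the uncovered set is narrow. A clinician supervises every clamp, an unexpected event that stops a clamp is covered, and further glucagon is withheld after vomiting judged likely to be due to it. The PI hears of events at once, and the external board receives adverse events under IX.c. Xeris glucagon had been given at 10 to 20 times this dose with only mild to moderate events. All of this stands, and it keeps the point small. The reassurance has limits, because those data were blinded and came from healthy volunteers, not people with type 1 diabetes.

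A second reply is that the institutional policy or FDA regulations may impose a pause. That also stands: the documents do not show it either way.

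A reader might infer that the DSMB would never learn of such an event, or that no independent review of it is required anywhere. The documents do not support either reading. IX.c contradicts the first, and the unseen external rules prevent the second. What is missing from the visible text is a deadline or a hold, not a reporting route.

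**Conclusion.** The point holds in limited form and is worth a small change. On the visible text, mandatory DSMB review before further dosing is keyed to discontinuation. A serious or unexpected, possibly related reaction in a completed clamp, or one first seen later, has a reporting route to the board but no review deadline and no hold.

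The size cannot be expressed as a number of subjects. The documents give neither a rate of such reactions nor a DSMB review time. A reader might divide a guessed delay by the average interval of about 8-15 days to count further clamps. That is not supported, because the delay would be invented and the actual spacing of clamps is not stated. The interval shows only that the expected pace is slow on average, with clustering possible.

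The conclusion rests on the natural reading of the hold sentence and on the visible text alone. The consequence is limited by the small doses and the supervision.

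**What to change.** Keep the existing sentence in IX.b and add:

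> Any serious adverse event, or any unexpected adverse event, judged at least possibly related to a glucagon injection or the clamp procedure and coming to the attention of study staff during the clamp or within a stated window after it (for example 7 days), will be notified promptly to the DSMB and reviewed (e-mail allowed) before the next clamp, whether or not the experiment was discontinued. Hypoglycemia and hyperglycemia that are not serious stay tied to discontinuation.

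Add a line defining a serious event, since the visible text has no definition. The relatedness test and the window keep an unrelated event weeks later from stopping the study.

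The cost is a causality judgment per event, an occasional extra review and a possible short delay to the next clamp. IX.b already allows e-mail or telephone meetings after the first DSMB meeting, so no new machinery is needed. One limit remains: the visible text describes no contact after discharge, so later events would be caught only if the subject reports them.
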